3.5.2. Outliers

Outliers will be identified during the data management and data analysis process, but no sensitivity analyses will be conducted. All data will be included in the data analysis.

3.6. Data Handling Conventions and Transformations

By-subject listings will be presented for all subjects in the Safety Analysis Set and sorted by unique subject ID number, visit date, and time (if applicable) unless otherwise specified. Data collected on log forms, such as AEs, will be presented in chronological order within subject.

Age (in years) on the date of the first dose of study drug and sex at birth will be used for analyses and presentation in listings.

If a subject was not dosed with study drug at all, then the date the informed consent was signed will be used instead of the first dose date of study drug.

Non-PK data that are continuous in nature but are less than the lower limit of quantitation (LOQ) or above the upper LOQ will be imputed as follows:

- A value that is 1 unit less than the LOQ will be used to calculate descriptive statistics if the datum is reported in the form of “< x” (where x is considered the LOQ). For example, if the values are reported as < 50 and < 5.0, values of 49 and 4.9, respectively, will be used to calculate summary statistics. An exception to this rule is any value reported as < 1 or < 0.1, etc. For values reported as < 1 or < 0.1, a value of 0.9 or 0.09, respectively, will be used to calculate summary statistics.
- A value that is 1 unit above the LOQ will be used to calculate descriptive statistics if the datum is reported in the form of “> x” (where x is considered the LOQ). Values with decimal points will follow the same logic as above.
- The LOQ will be used to calculate descriptive statistics if the datum is reported in the form of “≤ x” or “≥ x” (where x is considered the LOQ).

COBAS[®] AmpliPrep/COBAS[®] TaqMan[®] HCV Quantitative Test, v2.0 will be used to determine HCV RNA results in this study. The lower limit of quantitation (LLOQ) of the assay is 15 IU/mL.

When the calculated HCV RNA value is within the linear range of the assay, then the result will be reported as the “<< numeric value>> IU/mL.” This result will be referred to in this document as the numeric result or as “≥ LLOQ detected” for categorical result.

When HCV RNA is not detected, the result is reported as “No HCV RNA detected” or “target not detected”. This result will be referred to in this document as “< LLOQ target not detected” or “< LLOQ TND.”

When the HCV RNA IU/mL is less than LLOQ of the assay, the result is reported as “< 15 IU/mL HCV RNA detected”. This result will be referred to in this document as “< LLOQ detected.”

The overall category of HCV RNA < LLOQ includes “< LLOQ TND” and “< LLOQ detected.”

For numerical HCV RNA data, values below LLOQ will be set to the LLOQ 1 IU/mL (ie, 14 HCV RNA IU/mL). HCV RNA values returned as “No HCV RNA detected” will also be set to 14 IU/mL.

For selected analyses, HCV RNA data (IU/mL) will be transformed to the logarithmic (base 10) scale (\log_{10} IU/mL).

CCI
[Redacted]

CCI
[Redacted]

[Redacted]

[Redacted]

[Redacted]

[Redacted]

[Redacted]

[Redacted]

3.7. Analysis Visit Windows

3.7.1. Definition of Study Day

Study day will be calculated from the first dosing date of study drug and derived as follows:

- For postdose study days: Assessment Date – First Dosing Date + 1
- For days prior to the first dose: Assessment Date – First Dosing Date

Therefore, study day 1 is the day of first dose of study drug administration.

The last dose date will be the end date on study drug administration eCRF for the record where the “subject permanently discontinued” flag is ‘Y’. The last dose date will be defined as the maximum of the last dose dates of the study drugs. If there are subjects for whom the date of last study drug is unknown due to the reason that the subject was lost to follow-up and not able to be contacted, the date of last dose will be estimated using the maximum of nonmissing study drug start or stop dates, visit dates, and laboratory collection dates (posttreatment visits and unscheduled visits are not included).

3.7.2. Analysis Windows

Subject visits might not occur on protocol-specified days. Therefore, for the purpose of analysis, observations will be assigned to analysis windows.

In general, the baseline value will be the last nonmissing value on or prior to the first dose date of study drug.

HCV RNA, vital signs, and safety laboratory data collected up to the last dose date + 3 days are considered to be on-treatment data and HCV RNA, vital signs, and safety laboratory data collected after the last dose date + 3 days are considered posttreatment data. The analysis windows for on-treatment HCV RNA, vital signs and safety laboratory data are provided in [Table 1](#).

Table 1. Analysis Windows for On-treatment HCV RNA, Vital Signs and Safety Laboratory Data

Nominal Visit	Vital Signs			HCV RNA and Safety Laboratory Data		
	Nominal Day	Lower Limit	Upper Limit	Nominal Day	Lower Limit	Upper Limit
Baseline	1	(none)	1	1	(none)	1
Week 1	7	2	11	NA	NA	NA
Week 2	14	12	21	14	2	21
Week 4	28	22	42	28	22	42
Week 8	56	43	70	56	43	70
Week 12	84	71	≥ 85	84	71	≥ 85

HCV RNA, vital sign, and safety laboratory data collected after the last dose date + 3 days will be assigned to the posttreatment follow-up (FU) visits. Visit windows will be calculated from the last dose date (ie, FU Day = collection date minus the last dose date) as shown in [Table 2](#).

Table 2. Analysis Windows for Posttreatment HCV RNA, Vital Signs and Safety Laboratory Data

Nominal FU ^a Visit	HCV RNA			Vital Signs and Safety Laboratory Data ^b		
	Nominal FU Day	Lower Limit	Upper Limit	Nominal FU Day	Lower Limit	Upper Limit
FU 4	28	21	69	28	4	30
FU 12	84	70	146	NA	NA	NA

a FU x visit = posttreatment Week x follow up visit.

b Vital signs and safety labs will only be summarized for the FU 4 visit (up to 30 days after last dose).

ECG data collected up to the last dose date + 3 days are considered to be on-treatment data. Qualitative assessments of whether the ECG is normal or abnormal will be assessed based on the visit windows as shown in [Table 3](#).

Table 3. Analysis Windows for On-treatment ECG Data

Nominal Visit	Nominal Day	Lower Limit	Upper Limit
Baseline	1	(none)	1
Week 1	7	2	45
Week 12	84	46	87

Note: ECGs are to be collected at screening, baseline, Week 1, and Week 12 or Early Termination. For purposes of analysis, baseline will be the last available value prior to first dose.

3.7.3. Selection of Data in the Event of Multiple Records in an Analysis Visit Window

Depending on the statistical analysis method, single values may be required for each analysis window. For example, change from baseline by visit usually requires a single value, whereas a time-to-event analysis would not require 1 value per analysis window.

If multiple valid, nonmissing measurements exist in an analysis window, records will be chosen based on the following rules if a single value is needed:

- For baseline, the last nonmissing value on or prior to the first dosing date of study drug will be selected, unless specified differently. If there are multiple records with the same time or no time recorded on the same day, the baseline value will be the average of the measurements for continuous data, or the measurement with the lowest severity (eg, normal will be selected over abnormal for safety ECG findings) for categorical data.
- For postbaseline values:

The record closest to the nominal day for that visit will be selected except for HCV RNA posttreatment follow-up visits, for which the latest record in the analysis window will be selected.

If there are 2 records that are equidistant from the nominal day, the later record will be selected.

If there is more than 1 record on the selected day, the average will be taken for continuous data and the worse severity will be taken for categorical data, unless otherwise specified.

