7.5. Electrocardiogram Results

A Shift table of the investigator's assessment of ECG results at baseline (normal, abnormal but not clinically significant, abnormal and clinically significant, or missing) versus the investigator's assessment at each on-treatment visit (normal, abnormal but not clinically significant, abnormal and clinically significant, or missing) will be presented by treatment group. The number and percent of subjects in each cross-classification group will be presented (subjects with a missing value at baseline or on-treatment visit will not be included in the denominator for percent calculation).

A listing of ECG results including comments regarding clinically significant abnormalities will be provided.

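### Early-termination ECGs on Days 11–45 are displaced from the ECG shift table by the Week 1 ECG, and on-treatment ECGs after Day 87 have no window

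*SAP*

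**What the plan says.** SAP 3.7.2 defines on-treatment ECGs by reference to dosing: "ECG data collected up to the last dose date + 3 days are considered to be on-treatment data". Table 3 then gives the visit windows. Week 1 has nominal Day 7 and runs from Day 2 to Day 45. The next row reads "Week 12 84 46 87", that is, nominal Day 84, lower limit 46, upper limit 87. The note under the table says "ECGs are to be collected at screening, baseline, Week 1, and Week 12 or Early Termination", but the table has no row for early termination. Table 1, for vital signs, HCV RNA and safety laboratory data, leaves the last window open: "Week 12 84 71 ≥ 85 84 71 ≥ 85".

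For several records in one window, SAP 3.7.3 states: "The record closest to the nominal day for that visit will be selected except for HCV RNA posttreatment follow-up visits". Ties are settled by "If there are 2 records that are equidistant from the nominal day, the later record will be selected". The worse-severity rule in that section applies only to records on the same selected day.

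SAP 7.5 plans a shift table of the investigator's ECG reading at baseline against the "assessment at each on-treatment visit". Subjects missing at either time point are left out of the percentage denominator. A listing of ECG results is also planned. Protocol 6.5 requires an ECG at the early-termination visit.

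**The concern.** The early-termination ECG is collected by design but has no place of its own in the analysis windows. If the subject stops in the first half of treatment, that ECG falls in the Week 1 window and competes with the scheduled Week 1 ECG for a single slot judged by closeness to Day 7. Read together, the rules take the ECG recorded at stopping out of the only ECG summary that the SAP plans.

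The upper end has a different problem. On-treatment status follows the last dose, whereas the Week 12 window closes on a fixed study day, so a record can count as on-treatment and have nowhere to go.

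What is at stake is whether the ECG summary shows abnormalities recorded at early termination. For laboratory tests, SAP 7.2.2.2 classifies each subject by the most severe postbaseline grade, so a single bad value is picked up at whatever visit it occurs. ECGs have no such summary.

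**Working it through.** **Reproducing the Table 3 limits.** The midpoint of the nominal days is (7 + 84) / 2 = 45.5, which gives the 45/46 boundary. The upper limit is 84 + 3 = 87, which matches the ±3-day visit tolerance in Protocol 6.2. By the same tolerance, a Week 1 visit falls on Days 4–10 and a Week 12 visit on Days 81–87.

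**Termination ECG up to Day 45.** Assume that the ECG is within 3 days of the last dose.

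- A Week 1 ECG on Days 4–10 lies at most 3 days from Day 7.
- A termination ECG on Day 11 or later lies at least 11 − 7 = 4 days from Day 7.
- So on Days 11–45 the termination ECG always loses. With ECGs on Day 7 and Day 30, the distances are 0 and 23, and Day 7 is kept.
- Over every pairing of a Week 1 ECG on Day w = 4 to 10 with a later termination ECG up to Day 45, there are 41 + 40 + 39 + 38 + 37 + 36 + 35 = 266 combinations. The termination ECG is dropped in 254 (254/266 = 95.5%). The 12 exceptions all have it on or before Day 10. For example, Days 4 and 10 are both 3 days from Day 7, and the tie goes to the later record.
- If there is no Week 1 ECG, the termination ECG is kept but labelled Week 1.

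The displaced subject has no record on Days 46–87, so is missing at Week 12 and outside that denominator.

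**Termination ECG on Days 46–87.** It falls in the Week 12 window and is eligible for the table. With a Week 1 ECG on Day 7 and a termination ECG on Days 8–80, 38 of 73 days (52%) lead to displacement and 35 (48%) to retention. These are calendar days, not a forecast of the share of subjects.

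**ECG after Day 87.** For a last dose on Day L, on-treatment status ends on Day L + 3. A record after Day 87 needs L + 3 ≥ 88, so L ≥ 85.

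| Last dose | On-treatment days with no window |
|---|---|
| Day 84 or earlier | none |
| Day 85 | 88 |
| Day 86 | 88–89 |
| Day 87 | 88–90 |

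Dosing beyond Day 84 is possible. The regimen is 84 tablets (SAP 4.2.2) at no more than one per calendar day (Protocol 5.3.1 and 5.3.2), so a subject who misses a day and still finishes the supply ends after Day 84. The documents do not say how often this will occur.

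**Termination ECG more than 3 days after the last dose.** It is not on-treatment under SAP 3.7.2, and Table 2 has posttreatment windows for HCV RNA, vital signs and safety laboratory data only. It has no window on any study day. Protocol 3.3, 3.3.1 and 6.5 set no interval between the last dose and the termination visit.

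**The case against.** The strongest reply is that nothing is lost from the report. SAP 7.5 promises a listing of ECG results with comments on clinically significant abnormalities, and Protocol 8.2 says that individual data will be listed. With about 50 and 30 subjects and no testing, a reviewer can find a termination ECG in a listing. Protocol 8.5.4 asks for ECG summaries by cohort and visit, which the SAP delivers, and closest-to-nominal is its general postbaseline rule. An ECG after Day 87 also lies outside the protocol's own Week 12 tolerance. All of this stands. It limits the size of the point but does not remove it: a collected on-treatment ECG should not drop out of the only ECG summary through the way the windows happen to fall.

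Four stronger readings are tempting, and the documents do not support them.

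- A reader might infer that early discontinuers' last ECG is omitted in general. On-treatment termination ECGs on Days 46–87 are kept, and before Day 46 the loss needs a nearer ECG in the Week 1 window.
- A reader might take the Day 87 gap as part of the same problem. It concerns subjects dosed to Day 85 or later, who are not early discontinuers.
- A reader might say that the table would show such a subject as normal on treatment. It makes no overall statement: a normal Day 7 ECG appears, correctly, as normal at Week 1, and Week 12 is missing.
- A reader might link this to the primary safety endpoint. That endpoint, in Protocol 8.1.2, is an adverse event leading to permanent discontinuation. It is counted from adverse event records, and ECG windows cannot change it.

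**Conclusion.** The point holds as a small reporting gap. Table 3 and SAP 3.7.3 together keep an on-treatment termination ECG on Days 11–45 out of the shift table whenever a Week 1 ECG was taken on Days 4–10. A second, separate gap leaves on-treatment ECGs on Day 88 or later without a window when the last dose is on Day 85 or later, inconsistently with Table 1. A termination ECG more than 3 days after the last dose has no window at all.

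The conclusion assumes that the SAP rules are applied as written and that Week 1 visits are kept within the protocol tolerance. The number of subjects cannot be derived from the documents, which give no expected discontinuation rate or dosing overrun; it is probably small. Efficacy, adverse event counts and the ECG listing are unaffected.

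**What to change.** In SAP Table 3, change the Week 12 upper limit from 87 to ≥ 85, as in Table 1, bounded by last dose + 3 days. This closes the late gap but does nothing for early discontinuers.

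In SAP 7.5, add a shift from baseline to the worst postbaseline ECG assessment, using all postbaseline ECGs. State explicitly that the early-termination ECG is included even when it is taken more than 3 days after the last dose. A panel restricted to on-treatment records would still miss that case. The by-visit table can stay as it is.

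The cost is one table cell and one extra table panel. No new data are needed.

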4. SUBJECT DISPOSITION

4.1. Subject Enrollment and Disposition

A summary of subject enrollment will be provided by treatment group for each investigator. For each treatment group, the summary will present the number and percentage of subjects in the Safety Analysis Set. The denominator for the percentage calculation will be the total number of subjects analyzed for that column.

A summary of subject disposition will be provided by genotype and overall for each treatment group. This summary will present the number of subjects screened, the number of subjects enrolled, the number of subjects not enrolled, the number of subjects enrolled but never treated, and the number of subjects in each of the categories listed below.

- In Safety Analysis Set
- In Full Analysis Set
- In PK Analysis Set

- Completed study treatment
- Did not complete study treatment with reasons for premature discontinuation of study treatment
- Completed study
- Did not complete the study with reasons for premature discontinuation of study

Among subjects who completed study treatment or discontinued study treatment, the number and percentage of subjects will be summarized for the following:

- Subjects who had no HCV posttreatment Week 4 assessment and thereafter (No HCV FU-4 Assessment and thereafter)
- Subjects who had HCV posttreatment Week 4 assessment but no HCV posttreatment Week 12 and thereafter (With HCV FU-4 but No FU-12 and thereafter)

If a subject did not have any HCV RNA assessment ≥ 21 days after the last dose of any study drug (ie, lower bound of FU-4 visit for HCV RNA data), the subject is categorized as having “No HCV FU-4 and thereafter.” If a subject had the HCV FU-4 assessment but did not have any HCV RNA assessment ≥ 70 days after the last dose of any study drug (ie, lower bound of FU-12 visit for HCV RNA data), the subject is categorized as having “With HCV FU-4 but No FU-12 and thereafter.”

In addition, the total number of subjects who were enrolled, and the number of subjects in each of the disposition categories will be depicted by a flowchart.

The following by-subject listings will be provided by unique subject ID number in ascending order to support the above summary tables:

- Subjects Who Received Study Drug from Specific Batches
- Subject disposition

4.2. Extent of Study Drug Exposure and Adherence

Extent of exposure to study drug will be examined by assessing the total duration of exposure to study drug and the level of adherence relative to the study drug regimen specified in the protocol.

4.2.1. Duration of Exposure to Study Drug

Total duration of exposure to study drug will be defined as last dosing date minus first dosing date plus 1, regardless of any temporary interruptions in study drug administration, and will be expressed in weeks using up to 1 decimal place (eg, 4.5 weeks).

The total duration of exposure to study drug will be summarized using descriptive statistics (n, mean, SD, median, Q1, Q3, minimum, and maximum) and using the number (ie, cumulative counts) and percentage of subjects exposed through the following time periods: Baseline (Day 1), Week 1 (Day 7), Week 2 (Day 14), Week 4 (Day 28), Week 6 (Day 42), Week 8 (Day 56), and Week 12 (Day 84). A 3-day window is applied to the last planned on-treatment visit to match with the protocol-specified visit window, ie number of subjects exposed through Week 12 will be calculated as the number of subjects who were exposed to study drug for at least 81 days. Summaries will be provided for the Safety Analysis Set by HCV genotype and treatment group.

4.2.2. Adherence to Study Drug

The presumed total number of tablets administered to a subject will be determined by the data collected on the drug accountability CRF using the following formula:

$$\text{Total Number of Doses Administered} \\ \left(\sum \text{No. of Tablets Dispensed} \right) - \left(\sum \text{No. of Tablets Returned} \right)$$

The level of adherence to the study drug regimen will be assessed based on the total amount of study drug administered relative to the total amount of study drug prescribed at baseline.

The level of adherence will be expressed in percentage using the following formula:

$$\text{Level of Adherence (\%)} = \left(\frac{\text{Total Amount of Study Drug Administered}}{\text{Total Amount of Study Drug Prescribed at baseline}} \right) \times 100$$

Note: If calculated adherence is greater than 100%, the result will be set to 100%.

In this study, the total amount of SOF/VEL (400/100 mg) or SOF/VEL/VOX (400/100/100 mg) prescribed for 12 weeks would require 84 tablets.

Subjects who prematurely discontinue study drug for lack of efficacy (ie, virologic failure) will have the total amount of study drug prescribed calculated up to the first date when virologic failure criteria were met. For virologic failure confirmed by 2 consecutive measurements, the date of the first measurement will be used. If study drug bottles are dispensed on or after the subject first met virologic failure criteria, these bottles will not be included in the calculation of adherence. If a bottle is dispensed and the bottle is returned empty, then the number of tablets returned will be entered as zero. If a bottle is dispensed but not returned (missing), the number of tablets taken from that bottle will be counted as zero.

Descriptive statistics for the level of adherence (n, mean, SD, median, Q1, Q3, minimum, and maximum) with the number and percentage of subjects belonging to adherence categories (eg, < 80%, ≥ 80 to < 90%, ≥ 90%, at least 80% adherence to study drug) will be provided by treatment group for the Safety Analysis Set.

No inferential statistics will be provided for duration of exposure and adherence to study drug.

A separate by-subject listing of study drug administration and drug accountability will be provided by unique subject ID number (in ascending order) and visit (in chronological order).

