3.3.2. Virologic Response Based Treatment Stopping Criteria

The following on-treatment Virologic Response-based Treatment Stopping Criteria will be utilized:

- Confirmed HCV RNA \geq LLOQ after 2 consecutive HCV RNA $<$ LLOQ
- Confirmed $> 1 \log_{10}$ increase in HCV RNA from nadir
- HCV RNA \geq LLOQ through 8 weeks of treatment

Confirmation when required as described above should be performed as soon as possible and must occur no later than 2 weeks after an initial observation indicating virologic failure during the on-treatment phase.

Subjects who terminate study drug early due to virologic failure as defined above will complete the Early Termination (ET) visit and all posttreatment visits.

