5.2.2. Packaging and Labeling

5.2.2.1. Packaging and Labeling SOF/VEL FDC

SOF/VEL FDC (400/100 mg) tablets are packaged in white, high density polyethylene (HDPE) bottles. Each bottle contains 28 tablets and polyester packing material. Each bottle is enclosed with a white, continuous thread, child-resistant polypropylene screw cap with an induction-sealed, aluminum-faced liner.

SOF/VEL FDC bottles to be distributed to study centers in Korea shall be labeled to meet all applicable requirements of the Ministry of Food and Drug Safety (MFDS) guideline to Good Manufacturing Practice Annex 11 (Investigational Medicinal Products) and/or local regulations as applicable.

Sufficient quantities of SOF/VEL FDC tablets will be shipped to the investigator or qualified designee from Gilead Sciences Clinical Supply Management (or its designee).

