6.2.3. Weeks 4 and 8 (\pm 3 Days)

The following procedures/assessments are to be completed at the end of Week 4 and Week 8:

- Obtain vital signs (refer to Section 6.7.5)
- Assessment of AEs and concomitant medications
- Review of study drug adherence and dosing regimen including pill count
- Dispense study drug as directed by the IWRS (Week 4 only)
- Obtain blood sample for tests:

Hematology

Chemistry

Coagulation tests

HCV RNA

HCV resistance samples

HBV DNA Sample (only for HBcAb positive subjects at Screening)

Single PK (refer to Section 6.7.2.1)

- Obtain urine sample for:

Pregnancy test for females of childbearing potential only (refer to Section 6.7.10)

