4.4. Assessment of COVID-19 Impact

This study was ongoing during the novel coronavirus (2019 nCoV [COVID-19]) pandemic which has caused a disruption in the regular visit schedules for this study. Some subjects were unable to attend onsite visits due to shelter in place guidelines, site closures, or other reasons. This section provides how to handle special situations due to COVID-19 in the analysis.

Adverse events due to COVID-19 will be included in AE analyses if applicable.

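### For confirmed on-treatment failures, the SAP adherence formula counts tablets past the date at which its denominator stops, and it scores any unreturned bottle as zero tablets taken

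*SAP*

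**What the plan says.** SAP 4.2.2 defines adherence as tablets administered (dispensed minus returned) over tablets prescribed at baseline. The full course "prescribed for 12 weeks would require 84 tablets". Four further rules matter here:

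- **Denominator for failures.** For subjects who discontinue for virologic failure, the prescribed amount is "calculated up to the first date when virologic failure criteria were met". If failure is confirmed by two consecutive values, the date of the first is used.
- **Numerator for failures.** The only matching rule leaves out bottles dispensed on or after that date. It works by dispensing date, not by date of intake.
- **Cap.** The SAP states: "If calculated adherence is greater than 100%, the result will be set to 100" percent.
- **Unreturned bottles.** If a bottle does not come back, "the number of tablets taken from that bottle will be counted as zero". No matching reduction of the denominator is stated.

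Protocol 3.3.2 says that confirmation, where required, "must occur no later than 2 weeks after an initial observation indicating virologic failure during the on-treatment phase". Protocol 6.1.2, 6.2.3 and Appendix 2 schedule dispensing on Day 1 and at Week 4 only. SAP 3.3 and 6.1.3 then use adherence, cut at 80%, as a subgroup for SVR12 with exact confidence intervals and a forest plot.

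**The concern.** The ratio should compare tablets taken with tablets due over the same days. For a subject whose failure has to be confirmed, the denominator stops at the first failing sample while dosing, and hence the numerator, may run on. Each later tablet makes up on paper for an earlier missed one, and the cap removes the sign that something is amiss (a value above 100%). This happens only in subjects who have failed on treatment, where a reader most wants to tell missed doses from drug failure, and it moves them towards the ≥ 80% group.

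The unreturned-bottle rule works in the other direction. It turns missing accountability data into missed doses and can move a subject who took every tablet into the < 80% group. The adherence table and the SVR12-by-adherence subgroup could then both show people on the wrong side of the cut.

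**Working it through.** **Inputs from the documents.** One tablet daily for 12 weeks (Protocol 5.3); 84 tablets prescribed (SAP 4.2.2); 28 tablets per bottle for both products (Protocol 5.2.2.1 and 5.2.2.2); dispensing on Day 1 and at Week 4; confirmation within 14 days (Protocol 3.3.2); cut at 80% (SAP 3.3).

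**Assumptions.** First failing value on Day 56 (nominal Week 8); constant adherence *a*, so tablet counts are averages and may be fractional; last dose on Day *s*; no bottle lost in steps 2 and 3.

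**Step 1: the plan's own figure.** 12 × 7 × 1 = 84 tablets = 3 bottles of 28. It reproduces exactly.

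**Step 2: failure first seen on Day 56.** All scheduled bottles are out by Week 4, so the exclusion rule removes none. Reported adherence = min(100%, *a* × *s* / 56). With *a* = 75%:

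| Last dose | Tablets taken | Reported | Same period in both terms |
|---|---|---|---|
| Day 56 | 42 | 42/56 = 75.0% | 42/56 = 75% |
| Day 60 | 45 | 45/56 = 80.4% | 45/60 = 75% |
| Day 63 | 47.25 | 47.25/56 = 84.4% | 47.25/63 = 75% |
| Day 70 (14-day limit) | 52.5 | 52.5/56 = 93.8% | 52.5/70 = 75% |

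Four further days of dosing are enough to carry this subject over the 80% cut.

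**Step 3: range affected at the 14-day limit.** Reported = *a* × 70/56 = 1.25*a*. True adherence of 64% is reported as 80%, and 80% as 100%. Any constant adherence from 64% to just under 80% lands in the wrong group.

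**Step 4: lost bottles.** For a full adherer with *k* unreturned bottles, reported = (84 − 28*k*)/84:

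- *k* = 1: 56/84 = 66.7%
- *k* = 2: 28/84 = 33.3%

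Since 66.7% is the most that a completer with one unreturned bottle can score, any such completer falls below 80% whatever was taken.

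**Step 5: after correction.** With both terms run to last dose, the Day 70 case is 52.5/70 = 75%. With the lost bottle taken out of both terms, the full adherer is 56/56 = 100%.

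**The case against.** The strongest reply is that few subjects are touched and little depends on it. Adherence is descriptive, nothing is tested, the SVR12 subgroups are exploratory, and a by-subject listing of administration and accountability is planned. All of this stands and limits the weight of the point. It does not make the formula right.

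Other parts of the reply also hold:

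- **Safeguards.** The bottle-exclusion rule limits the excess for earlier failures, though it does not always remove it. With a failing value on Day 28 and one bottle dispensed on Day 1, a 75% adherer has taken 21 tablets; finishing the other 7 afterwards gives 28/28 = 100%. For Week 8 non-response, where Protocol 3.3.2 mentions no confirmation, the mismatch is zero if drug stops that day. Relapsers who completed treatment keep the 84-tablet denominator and are unaffected.
- **Choice of end date.** Doses after the failing sample cannot explain the failure, so stopping at that sample is a reasonable choice. The numerator would then have to stop there too, which the SAP does not arrange.
- **Lost bottles.** SAP 4.4 reports that "Some subjects were unable to attend onsite visits due to shelter in place guidelines, site closures, or other reasons". That shows missed visits, not lost bottles, and Appendix 2 of the Protocol asks subjects to bring all bottles back at every later visit.

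Three stronger readings are tempting but not supported:

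- *A 75% adherer is shown as 100%.* At Day 56 this can be built from 42 of 56 tablets followed by 14 daily ones, giving 56/56. Over the 70 days covered, that subject took 56/70 = 80% and belongs in the ≥ 80% group when both terms run to last dose. At constant 75% the figure at the 14-day limit is 93.8%.
- *About four subjects are at stake.* The planned 95% SVR12 implies 5% × 80 = 4 subjects without SVR12, but SAP 6.2.2 divides these into on-treatment failure, relapse and other. The documents give no expected number of on-treatment failures.
- *Scoring an adverse-event stop on Day 56 as 56/84 is a mistake.* It follows the stated definition relative to the amount prescribed at baseline. Exposure duration and treatment-completion status are reported separately.

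**Conclusion.** The point holds in a limited form. As written, SAP 4.2.2 overstates adherence for subjects who stop drug for a confirmed on-treatment failure and keep dosing beyond the first failing sample. In the Week 8 case a constant 75% adherer is reported at 84.4% to 93.8% for 7 to 14 further days, and so crosses the 80% cut. These figures rest on the assumed Day 56 sample, constant adherence and the stop dates shown; the documents fix none of them beyond the 14-day confirmation limit. The lost-bottle figures, 66.7% and 33.3%, need no assumption about dates.

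The consequence is confined to the adherence summary and the < 80% / ≥ 80% SVR12 subgroup. The overall SVR12 estimate and its interval do not change. The documents do not show how often either case arises, so they do not support a claim that the subgroup result will be materially distorted.

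**What to change.** In SAP 4.2.2:

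1. For virologic-failure discontinuations, use one period in both terms. Set prescribed tablets = last dose date − first dose date + 1, count all dispensed bottles, and delete the sentence that excludes bottles dispensed on or after the failure date.
2. Report the number of subjects with unreturned bottles. Repeat the adherence summary and the < 80% / ≥ 80% SVR12 subgroup with those bottles removed from both terms: 28 tablets off the denominator where it is 84, and for a virologic-failure stop the tablets that bottle was due to supply up to the last dose.

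The definition for other early stoppers can stay as it is. The cost is a small change to one derivation and one extra sensitivity column. Dose dates and accountability counts are already collected, and SAP 4.2.1 already computes the same interval as duration of exposure.
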